### 5.3.2. Secondary objectives

#### Cross-sectional study:

- To evaluate the relation between different sociodemographic factors and presence of infection by means of calculation of the adjusted prevalence ratios in different groups.

#### Cohort study:

- To evaluate the incidence (number of new cases of infection by number of participants and observation time, i.e. incidence rates per person-days). Participants with positive result at the first testing will not be included in this assessment.
- To evaluate the relation between different sociodemographic factors and incidence (rate ratios).
- To evaluate the dynamics of immune response:
  - cumulative seropositivity, i.e. proportion of positive tests at each moment;
  - cumulative seroconversion, i.e. cumulative proportion of participants at all moments with at least 1 positive test;
  - cumulative seroreversion, i.e. cumulative proportion of participants at all moments with at least 1 negative test after at least 1 positive test.

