## List of Appendices

**Appendix 1. Questionnaire for telephonic survey.**

**Appendix 2. Medical questionnaire.**

**Appendix 3. SARS-CoV-2 antibody test results.**

**Appendix 4. Participant Information Sheet and Informed Consent Form.**

## **1. Introduction**

Population analysis of infection spreading is one of the key methods of new epidemics control. The World Health Organization has included population serological surveys, which help to visualize the new virus distribution, into a list of essential assessments during the current epidemics, along with the vaccine development and search for effective treatments for severe disease. Such studies help understand real disease spread and a real proportion of fatal outcomes among the patients with a disease and infected persons. Initial studies have shown the presence of immune response to an earlier SARS-CoV-2 infection.

Regarding the SARS-CoV-2 pandemic, the population assessment of immune response is recommended until the year 2024, as currently there is a discussion of a high risk of second and further peaks of new coronavirus epidemics. Initial studies performed in the state of New York have shown that up to 14% state residents and 21.2% of New York City residents had had the infection and had developed antibodies. In the states of Idaho and California, there were not more than 2% of such people.

To evaluate the proportion of people who have had the disease in a whole population (a city, a region, a country), the representativeness of a sample needs a strict approach. The methodology of a serological study is in many aspects similar to a sociological survey but is more complicated due to the use of serological test results. In addition, the population characteristics of these tests, i.e. sensitivity and specificity, are not always well-known. A serological study sample should be representative for the general population (age groups, gender, place of living, mobility during the epidemics).

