## **2. Study objectives**

### **2.1.Primary objective**

**Pilot study:** to evaluate the proportion of people in St. Petersburg, Russia who have had the SARS-CoV-2 infection by means of analyzing the results of the blood serum tests for antiviral antibodies.

**Cohort study:** to evaluate the dynamics of the SARS-CoV-2 infection spread (incidence) by means of analyzing the results of blood serum tests for antiviral antibodies.

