## 3. Study procedures

### 3.1.Study design

This non-interventional observational socioepidemiological population study will be conducted in residents of St. Petersburg, Russia. Selection and invitation of participants will take place during telephonic survey. After giving signed informed consent, each participant will be subjected to a blood test for SARS-CoV-2 antibodies and will answer a questionnaire. The testing will be performed primarily using serological assays for serum IgG approved in the Russian Federation (Abbott Architect IgG and Genetico).

This study involves a telephonic sociological survey during which respondents will be invited to undergo a blood test for SARS-CoV-2 antibodies at the participating investigational sites in different cities and towns of Russia. The participants will undergo such a test, take part in an additional survey for those who plans or have already done such a test, and receive the results. A part of participants will be offered to use a taxi (see Section 5.2). Testing and questionnaire at the clinic will be repeated several times. It is planned to perform up to 10 visits which will include blood sampling, testing, and collection of additional information.

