**Table. Calculation of the study sample taking into account approximately 5% attrition at each visit**

	First visit	Week 4	Week 8	Week 12	Week 16	Week 20	Week 24	Week 28	Week 32	Week 36
Telephone-based questionnaire; medical hypothesis; IgG tests	1000	950	902	857	815	774	735	698	663	630

Study participants will be asked to undergo multiple tests for SARS-CoV-2 antibodies with 4-week intervals to assess the immune response dynamics. If a participant agrees to repetitive tests, they will also complete questionnaires with the objective of collecting epidemiological information for the period since the first test. Time of each round of survey and information collection will not exceed 4 weeks.

If the test is not performed in the mentioned interval, delayed testing data may be used. If before the initial or a later test a participant shows signs of acute respiratory infection (see Section 3.2.2.3) or has been diagnosed with COVID-19, the study will use results of

a test performed at least 2 days after all symptoms resolved, or results of the last negative test for the virus.

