#### **5. Statistical analysis**

##### **5.1. Sample**

In this study, a population of a region with the size of  $N$  is being looked at. Assuming that the number of infected ( $K$ ) in the population is distributed binomially and the serological test is ideal, 2-sided 95% Wilson confidence interval for the prevalence ( $p$ ) is:

$p' \pm z_{0,025} \sqrt{\frac{p'(1-p')}{n+4}}$ , where  $p' \equiv \frac{k+2}{n+4}$ , and  $z_{0,025}$  is the critical level of the standard normal distribution. In this case the sample size  $n$ , needed for the sample error to not exceed  $M$ , with a conservative assumption of hypothetical prevalence of 50%, is:  $n > \left(\frac{1,96 \times 0,5}{M}\right)^2 - 4$ . For the sample error to reach 2%, at least 2397 observations are needed.

If we assume that hypothetical prevalence is 10%, the sample size is less than 900 for the sample error of 2%. Taking into account possible attrition at the repetitive tests, it is planned to enroll at least 1000 participants.

During the study, it is planned to test at least 1000 participants with a highly sensitive (Se) and highly specific (Sp) test, to reach the sample error level of 2%. The calculations above are applicable to a cross-sectional study. In a cohort study, there is a problem of the sample attrition. We assume loss of 5% of participants at the repetitive blood sampling. If 1000 participants provide samples at the first visit, there will be 630 tested participants at Week 36.

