**11. Do you regularly (continuously) receive any medications not mentioned above?**

- ☐ No ☐ Yes (please list all medications that you remember of)

**12. Were you ever diagnosed with a cancer?** ☐ No ☐ Yes

If yes, did you receive oncological treatment during the last year? ☐ No ☐ Yes

**13. Do you have any known allergies?** ☐ No ☐ Yes

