**QUESTIONS FOR WOMEN**

**14. Are you currently pregnant?** ☐ No ☐ Yes (how many weeks)

**15. Did you give birth during the last year?** ☐ No ☐ Yes (when) \_\_\_\_\_

Completion date \_\_\_\_ May/June (underline the applicable option) 2020

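### Antibody-based case counting runs into early 2021 with no provision for vaccination, so vaccine-induced positives could be counted as new infections in the late cohort rounds

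*Protocol*

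**What the plan says.** The cohort's primary objective (Protocol 2.1) is "to evaluate the dynamics of the SARS-CoV-2 infection spread (incidence) by means of analyzing the results of blood serum tests for antiviral antibodies". Section 5.3.1 has the cohort compare prevalence between time points. Section 5.3.2 defines incidence as the "number of new cases of infection by number of participants and observation time", expressed per person-days, and the only people it leaves out are those positive at the first test.

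On timing, section 3.1 states "Study participants will be asked to undergo multiple tests for SARS-CoV-2 antibodies with 4-week intervals" and "It is planned to perform up to 10 visits which will include blood sampling, testing, and collection of additional information". Its table ends at Week 36, and late tests may be used. The questionnaire in Appendix 2 carries the completion date "May/June (underline the applicable option) 2020". Section 3.1 also says that the clinic questionnaire is repeated.

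The only reference to a COVID-19 vaccine is in the introduction, where population serosurveys are listed as essential "along with the vaccine development and search for effective treatments for severe disease". The eligibility criteria (3.2), the telephone survey (Appendix 1) and the medical questionnaire (Appendix 2) do not ask about vaccination or participation in a vaccine trial. The nearest item, number 11 of Appendix 2, asks: "Do you regularly (continuously) receive any medications not mentioned above". Section 4 names two assays and does not say which antigen either one targets.

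**The concern.** A serological cohort can read new positivity as new infection only while infection is the sole source of antibody. The protocol itself notes that vaccines are in development and plans follow-up into early 2021, so vaccination of some participants, perhaps within a trial, was foreseeable. A participant who is negative, is vaccinated and then tests positive would, on the natural reading of 5.3.2, be a new case, and would add to the prevalence that 5.3.1 compares over time. The late rounds would then mix infection with vaccination. If uptake differs by age or occupation, the rate ratios by sociodemographic factor in 5.3.2 would be distorted as well. An analysis rule written later cannot separate the two sources if vaccination dates were never collected.

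**Working it through.** **Inputs from the protocol.** 1000 at the first visit; 5% loss per repeat visit; nine repeat visits at 4-week intervals; 10% hypothetical prevalence (5.1); May/June 2020 start (Appendix 2).

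**Assumptions, not in the protocol.** True seroconversion of 1% of remaining negatives per 4 weeks; a share v of those still uninfected vaccinated in the last interval; a probability s that the assay detects vaccine antibody.

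**1. The plan's own figure.** 1000 × 0.95^9 = 630.2. Section 5.1 says "If 1000 participants provide samples at the first visit, there will be 630 tested participants at Week 36", so the figure reproduces.

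**2. Calendar.** 1 May 2020 + 36 weeks = 8 January 2021. 30 June 2020 + 36 weeks = 9 March 2021.

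**3. Negatives at risk in the last interval.** 630.2 × 0.90 × 0.99^8 = about 523. The simpler 630 × 0.90 = 567 ignores the conversions already assumed in the eight earlier intervals.

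**4. Last interval only.** True cases: 523 × 0.01 = 5.2. Vaccine positives: 523 × 0.99 × v × s. Ratio: (0.01 + 0.99 × v × s) / 0.01.

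**5. Whole follow-up.** True cases are the sum over k = 1 to 9 of 900 × 0.95^k × 0.99^(k−1) × 0.01:
8.55 + 8.04 + 7.56 + 7.11 + 6.69 + 6.29 + 5.92 + 5.57 + 5.23 = about 61.
Ratio: (61 + vaccine positives) / 61, taking person-time as unchanged.

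| v (s = 1) | Vaccine positives | Ratio, last interval | Ratio, whole follow-up |
|---|---|---|---|
| 1% | 5.2 | 2.0 | 1.1 |
| 5% | 25.9 | 6.0 | 1.4 |
| 10% | 51.8 | 10.9 | 1.85 |

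The last entry is about 1.9 (1.86) if the small factor 0.99 is dropped. At s = 0.5 the vaccine positives halve. At v = 0 or s = 0 every ratio is 1.

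**6. Prevalence at Week 36.** The assumptions above imply a true value of 1 − 0.90 × 0.99^9 = 17.8%; take 20% as a round figure. Observed prevalence is p + (1 − p) × v × s, where v is now cumulative uptake among the uninfected. With v = 5% and s = 1 it rises by 0.80 × 0.05 = 4.0 points, about 25 of 630 people. The 95% half-width by the formula in 5.1 is 1.96 × √(0.20 × 0.80 / 634) = 3.1 points. With v = 1% the rise is 0.8 points, well inside that half-width.

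**The case against.** The strongest objection is that the harm rests on two facts the protocol does not supply: that participants are vaccinated before Week 36, and that the assays detect vaccine antibody. This stands. A reader might infer that vaccine antibodies would be counted as infections; the text supports only that they could be. Nor does the introduction's remark about antibody surveys until 2024 lengthen this cohort, which is capped at ten visits.

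Second, a reader might infer that nothing collected could identify vaccinated participants. That goes too far. Section 3.1 foresees follow-up questionnaires covering the period since the first test, and sections 3.2.1 and 3.2.2 allow transfer of clinic medical data. Either might capture vaccination. However, the clinic questionnaire that is shown is to be repeated and has no such item, clinic data may be refused, and no section requires vaccination to be recorded.

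Third, the protocol never states that every new positive is a new infection, and case definitions and censoring rules often sit in an analysis plan, which is not shown here. This is fair as to the rule. It does not answer the missing variable. The seropositivity and seroconversion summaries in 5.3.2 remain correct descriptions whatever the source of antibody; the incidence estimate does not.

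Fourth, ratios of 2, 6 and 11 place all uptake in one interval. Quoted alone they would overstate the effect on incidence over the whole follow-up, so both sets are given.

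**Conclusion.** The point holds in conditional form. Infection is inferred from antibody results through January to March 2021, and nothing shown in the protocol provides for vaccination during that time. Any vaccinated converter whom an assay detects could be counted as a new infection. The exposure lies in the late cohort rounds; the May/June 2020 round is essentially unaffected.

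The size cannot be determined from the protocol. Under the stated assumptions, incidence in the last interval is inflated about 2 to 11 times and whole-follow-up incidence about 1.1 to 1.9 times, for uptake of 1% to 10% with full detection. At 5% cumulative uptake with full detection, the rise in Week 36 prevalence (4.0 points) exceeds the sampling half-width (3.1 points). With no uptake, or an assay blind to vaccine antibody, there is no bias. The change is worth making because the missing item may not be recoverable later: the plan itself expects 370 of 1000 participants to be lost by Week 36.

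**What to change.** 1. Add one item to the questionnaire at visits 2 to 10: receipt of any SARS-CoV-2 vaccine, including within a trial, with the date of each dose.
2. In section 4, state which antigen each assay detects, so that it is clear whether vaccine antibody can register on it.
3. In 5.3.1 and 5.3.2, for any assay that can detect vaccine antibody, base infection prevalence and incidence on results up to the first dose, with person-time censored at that date. Report later results separately, as seropositivity from infection or vaccination.

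The cost is one question per visit, one sentence on the assays and a short analysis rule. The downside is some loss of late person-time, and only if vaccination occurs.

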#### **4. Laboratory diagnostics**

To measure IgG antibodies titer, Abbott Architect SARS-CoV-2 IgG (<https://www.fda.gov/media/137383/download>) assay will be used. According to the manufacturer, the sensitivity of the assay is 100%, and the specificity is 99.6%. With a scientific objective, Coronapass Total Ig assay (Genetico) will also be used, with the sensitivity of 96% and specificity of 100%, according to the manufacturer. Other point-of-care tests can be used to immediately inform participant but not for the research analysis.

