(A SINGLE ANSWER) DisableReordering Single choice from 'Q8 list'

1       Yes

2       No

Q9     Single choice from 'Q9 list'

Q8=1

How often have you been outdoors during the last week (7 days)?

(A SINGLE ANSWER)

Q10 Single choice from 'Q10 list'

Q8=1

How much time have you spent out of your home when you went out most recently?

(IF THE ANSWER CONTAINS INTERVAL, REGISTER THE UPPER BORDER.

REGISTER HOURS OR MINUTES — 30 min, 20 min

IF THE ANSWER CONTAINS HOURS AND MINUTES, REGISTER AS IT IS: 1 h 10 min, 2 h 40 min)

999 (DON'T READ) Not sure

Q11 Multiple choice from 'Q11 list'

Q8=1

Which of the following places have you visited during the last week?

(ANY NUMBER OF ANSWERS)

1 Work

2 Metro and other public transport, including taxi

3 A pharmacy

4 A shop or a market

5 A post office, a bank, an ATM, a medical institution

6 I have not been to any of these places

Q12

Have you had any examination for coronavirus?

(DON'T READ ANSWERS)

(A SINGLE ANSWER) DisableReordering,

Blocking

Single choice from 'Q12 list'

1 Yes

2 No

Q121 Single choice from 'Q121 list'

Q12=1

The result of this examination was:

(A SINGLE ANSWER)

1 Positive

2 Negative

3 I don't know

999 (DON'T READ ANSWERS) Not sure

Q13 Single choice from 'Q13 list'

Do you or do you not follow information regarding coronavirus? If you follow, do you do it continuously or once in a while?

(DON'T READ ANSWERS)

(A SINGLE ANSWER)

1 Follow continuously

2 Follow once in a while

999 (DON'T READ ANSWERS) Not sure DisableReordering

Q15 Single choice from 'Q15 list'

Q8=1

Were you wearing a mask when leaving your home during the last week?

(DON'T READ ANSWERS)

(A SINGLE ANSWER)

1 Yes

2 No

Q16 Single choice from 'Q16 list'

Q8=1 and Q15=1

Were you wearing a mask while just outdoors?

(DON'T READ ANSWERS)

(A SINGLE ANSWER)

1 Yes

2 No

Q17

Can you say that now you wash your hands more often than before the epidemics?

(DON'T READ ANSWERS)

(A SINGLE ANSWER) Single choice from 'Q17 list'

1 Yes

2 No

999 (DON'T READ) Not sure

Q19

In your opinion, should the limitations for public have been stricter or not?

(DON'T READ ANSWERS)

(A SINGLE ANSWER) DisableReordering Single choice from 'Q19 list'

1 Yes, they should have been

2 No, they should not have been

999 (DON'T READ) Not sure DisableReordering

Q20 Single choice from 'Q20 list'

Q19=2

In your opinion, should the limitations for public have been less strict or not?

(DON'T READ ANSWERS)

(A SINGLE ANSWER)

1 Yes

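### The incidence risk set keeps participants with a known earlier COVID-19 infection whose first antibody test is negative

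*Protocol*

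**What the plan says.** **Risk set.** Protocol section 5.3.2 (Cohort study) defines incidence as "number of new cases of infection by number of participants and observation time, i.e. incidence rates per person-days". Its only rule on who is left out is "Participants with positive result at the first testing will not be included in this assessment".

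**How infection is ascertained.** Section 2.1 gives the cohort's objective as "to evaluate the dynamics of the SARS-CoV-2 infection spread (incidence) by means of analyzing the results of blood serum tests for antiviral antibodies".

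**Who may enter.** Section 3.1 foresees earlier illness: "If before the initial or a later test a participant shows signs of acute respiratory infection" "or has been diagnosed with COVID-19, the study will use results of" "a test performed at least 2 days after all symptoms resolved". As an alternative it accepts the last negative virus test. Such a person is deferred, not removed. Among the exclusion criteria in section 3.2.2, the only one tied to infection is acute respiratory symptoms at the time of a survey or test.

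**What is collected.** Appendix 1, Q12, asks "Have you had any examination for coronavirus", and Q121 records whether the result was positive. The incidence rule uses neither.

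**The concern.** Incidence should relate new infections to the time of people who could still have a first infection. A negative first antibody test does not establish that when the participant is already known to have been infected. The 2-day minimum in section 3.1 deals with acute illness; it does not ensure that antibodies are detectable by then.

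A diagnosed participant who is negative at the first visit and positive at Week 4 would be dated to the first follow-up interval, although the infection came before entry. If there were enough of them, early incidence would look too high and the later course would look like a decline. The rate ratios for sociodemographic factors in 5.3.2 would naturally use the same cases and person-time.

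**Working it through.** **1. What the documents supply.** The protocol states no figure for the incidence risk set, so there is none to reproduce. Its retention figure, used below, does reproduce: 1000 × 0.95^9 = 630.2, against 630 in section 5.1. Other inputs are a 10% planning prevalence (5.1), 4-week intervals (3.1), and manufacturer sensitivities of 100% (Abbott) and 96% (Coronapass) from section 4. The number of known earlier cases, their share negative at entry, the share converting by Week 4 and the true incidence are not given. Values for these are assumptions.

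**2. First-test negatives implied by the stated sensitivities.** Assume 10 to 30 of 1000 entrants are known earlier cases.
- Abbott: (10 to 30) × (1 − 1.00) = 0.
- Coronapass: 10 × 0.04 = 0.4, up to 30 × 0.04 = 1.2.

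People tested before they have converted would add to this by an unknown number.

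**3. Effect on the rate for an assumed m = 4.** Take 900 people truly at risk (1000 less 10%), nine 28-day intervals, 5% loss per visit and true incidence λ per interval. In each interval:
- retained = 0.95 × previous number at risk
- events = λ × retained
- person-days = 28 × (retained − events) + 14 × events

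The m earlier cases are added on top. At Week 4, 0.95 × m are retained and a share c of them converts, contributing 14 person-days each. The rest stay negative and add 28 person-days per interval, with the same loss. Rates are per 100,000 person-days.

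| λ | c | Events / rate, m left out | Events / rate, m kept | Overall ratio | First-interval events, kept / left out |
|---|---|---|---|---|---|
| 1% | 1 | 61.0 / 35.89 | 64.8 / 38.12 | 1.062 | 12.35 / 8.55 = 1.44 |
| 1% | 0.5 | 61.0 / 35.89 | 62.9 / 36.92 | 1.029 | 10.45 / 8.55 = 1.22 |
| 3% | 1 | 170.2 / 108.77 | 174.0 / 111.17 | 1.022 | 29.45 / 25.65 = 1.15 |
| 3% | 0.5 | 170.2 / 108.77 | 172.1 / 109.69 | 1.008 | 27.55 / 25.65 = 1.07 |

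The first-interval counts come from 900 × 0.95 × λ = 8.55 or 25.65 true events, plus 4 × 0.95 × c = 3.8 or 1.9 false ones.

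**4. Opposite direction.** If none of the 4 converts, they add only person-time: 4 × 28 × (0.95 + 0.95² + … + 0.95^9) = 112 × 7.025 = 787 person-days. The rate is then multiplied by 169,847 / (169,847 + 787) = 0.995 at λ = 1%, and by 156,464 / (156,464 + 787) = 0.995 at λ = 3%, a fall of about 0.5%.

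**5. At the top of step 2.** With m = 1.2 and all converting, false events are 1.2 × 0.95 = 1.14. Against 61.0 and 170.2 true events over the whole follow-up, that is about 1.9% and 0.7%.

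**The case against.** Taking people who are antibody-negative at baseline is the ordinary starting point for a serological cohort, and it fits an objective that measures incidence by antibody tests. A statistical analysis plan may exist and could refine the case definition. That is fair, but 5.3.2 does more than stay silent: it states a rule, and a plan that followed it would inherit the gap.

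Several stronger readings are tempting, and the documents do not support them:

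- **That the protocol expressly counts these conversions as new infections.** It does not define a new case as a first positive after a negative. That follows from reading 2.1 and 5.3.2 together. One could answer that an infection diagnosed before entry is plainly not new.
- **That first-interval incidence is inflated severalfold.** This needs a sizeable share of known cases to be antibody-negative at entry. The documents give no such share, and their own sensitivities give 0 to 1.2 people.
- **That participants who have already lost antibodies are expected and drive the bias.** Section 2.2 lists seroreversion as something to evaluate. Someone who has reverted is also not an obvious candidate to turn positive at Week 4.
- **That the collected data prove infection before entry.** Q12 and Q121 are self-reported, with no test type or date, and an acute respiratory infection need not be SARS-CoV-2. Only the diagnosed subgroup is properly known.
- **That the cohort's main result is compromised.** Section 2.1 mentions incidence, but 5.3.1 makes the main analysis a comparison of prevalence over time, which this rule does not touch.
- **That the use of two assays is part of the same defect.** Section 4 says "Coronapass Total Ig assay (Genetico) will also be used", and 5.3.2 does not say which assay defines a positive. That is a separate ambiguity.

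The exclusion of people with current symptoms also shrinks the recently infected group, and 2 days is a minimum, not the expected delay.

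**Conclusion.** The concern holds in a limited form. The stated rule leaves known earlier cases with a negative first test in the risk set, and no other section takes them out. Later converters among them would probably be counted as new, mostly in the first interval; those who stay negative pull the rate down slightly.

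The size cannot be derived from the documents. For an assumed 4 such participants, at least half of whom convert by Week 4, and 1% to 3% true incidence per 28 days, the whole-study rate rises by about 1% to 6% and the first-interval count is 1.07 to 1.44 times the true one. Four is more than the stated sensitivities alone imply for 10 to 30 known cases. If every earlier case were positive at entry, the effect would be zero. This is an inexpensive correction to a secondary analysis and does not threaten the study's main result.

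**What to change.** In 5.3.2, define the incidence risk set as participants who are negative at the first test, report no earlier positive coronavirus examination (Q121 = 1) and have no COVID-19 diagnosis before the first test. The diagnosis clause is needed because Q121 is asked by telephone before the clinic visit. Use the same assay to define baseline negativity and later conversion.

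Add two sensitivity analyses:
- the rule as 5.3.2 now states it, to show how much the choice matters;
- risk time starting at the second negative test, which addresses undiagnosed late converters whom the revised definition cannot identify.

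The cost is a short change to the text. It needs no new visits: Q121 is already asked, and section 3.1 already needs to know about earlier diagnoses. A few participants leave the denominator. Because Q121 is self-reported without test type or date, some will be removed wrongly and some earlier cases will be missed.

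### Cumulative seroconversion and seroreversion are defined as simple proportions without an at-risk set or censoring; taken literally, with the planned dropout, both understate the risk of a new event

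*Protocol*

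**What the plan says.** Protocol section 2.2 makes individual immune dynamics (seroconversion and seroreversion) a secondary objective. Section 5.3.2, Cohort study, defines the two cumulative measures. The first reads "cumulative seroconversion, i.e. cumulative proportion of participants at all moments with at least 1 positive test". The second takes the same form but asks for a reversal of the earlier result; it is given as the "cumulative proportion of participants at all moments with at least 1 negative test after at least 1 positive test".

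Neither definition states a denominator over time, an at-risk set or a rule for people who leave. The incidence item in the same list does use observation time, as rates per person-days, and leaves out participants who are positive at the first test. That exclusion is attached to the incidence item only.

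The follow-up is fixed elsewhere. Section 3.1 says: "It is planned to perform up to 10 visits which will include blood sampling, testing, and collection of additional information". Tests are 4 weeks apart. The table in that section is headed "Calculation of the study sample taking into account approximately 5% attrition at each visit", and section 5.1 adds: "If 1000 participants provide samples at the first visit, there will be 630 tested participants at Week 36". Section 5.1 calls attrition a problem of the cohort study, but answers it only through the number enrolled.

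**The concern.** A person who leaves without the event can no longer show it. If that person stays in the denominator up to Week 36, any later event is silently counted as no event, and the cumulative proportion falls below the cumulative risk by an amount that grows with each visit. The curve then flattens partly because people leave.

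Seroreversion has a second problem, staggered entry. Someone first positive at Week 32 has one later test in which to revert, and someone positive at the first visit has nine. A simple proportion weights them alike.

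At stake is the description of immune dynamics. Seroreversion that reads too low makes antibodies look more durable than they are. The cumulative seroconversion figure could also disagree with the person-days incidence from the same data. Section 6 foresees press releases, preprints and public data for epidemic modelling, so these figures may be reused.

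**Working it through.** **Plan's own figure.** Nine repeat visits at 5% loss: 1000 × 0.95^9 = 630.2, which matches the 630 in sections 3.1 and 5.1. The loss is 37.0%.

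**Inputs.** From the protocol: 9 rounds, retention s = 0.95 per round, and 10% prevalence (a planning value in section 5.1). Assumed, because the protocol gives none: seroconversion risk h per round of 1%, 2% or 5%, constant over time; reversion risk r of 3% per round; dropout unrelated to infection; all ten visits held.

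**Seroconversion among baseline negatives.**
- True risk at Week 36: 1 − (1 − h)^9.
- Literal proportion over all participants: sum over k = 1 to 9 of h(1 − h)^(k−1) × 0.95^k.

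| h per round | True | Literal | Relative shortfall |
|---|---|---|---|
| 1% | 8.65% | 6.77% | 21.7% |
| 2% | 16.63% | 13.07% | 21.4% |
| 5% | 36.98% | 29.37% | 20.6% |

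Timing matters. For a true 36-week risk of 10%, using the retention in the plan's table, the shortfall is 17% if events decline linearly over the nine rounds (weights 9 to 1) and 27% if they rise linearly (weights 1 to 9).

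**The measure as worded, with 10% baseline positives counted** (0.10 + 0.90 × the values above):

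| h per round | True | Literal | Relative shortfall |
|---|---|---|---|
| 1% | 17.8% | 16.1% | 9.5% |
| 2% | 25.0% | 21.8% | 12.8% |
| 5% | 43.3% | 36.4% | 15.8% |

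**Other denominators, baseline negatives, h = 2%.**
- Ever-positives among those tested at Week 36, numerator and denominator both restricted: 16.6%, the true value.
- All ever-positives, leavers included, divided by those still attending: 0.1307 / 0.6302 = 20.7%. This is not strictly a proportion, because the numerator is not contained in the denominator.

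**Seroreversion, h = 2%, r = 3%, 10% positive at entry.**
- True 36-week risk from first positive test: 1 − 0.97^9 = 24.0%.
- Observed first positives at visit k: e_0 = 0.10, and e_k = 0.90 × h(1 − h)^(k−1) × s^k for k = 1 to 9.
- Observed reversion with m = 9 − k rounds left: R_m = sum over j = 1 to m of r(1 − r)^(j−1) × s^j.
- Proportion among ever-positives: sum of e_k × R_(9−k), divided by the sum of e_k.
- No dropout (s = 1): 0.0413 / 0.2496 = 16.5%.
- Planned dropout (s = 0.95): 0.0313 / 0.2176 = 14.4%, a shortfall of about 40%.
- Divided by all participants: 3.1%, which is not a risk of reversion at all.

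The same formula with r and h each set to 1% and 5% as well gives shortfalls between 34% and 46%.

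**The case against.** The strongest reply is that these are one-line descriptive definitions. They never say that leavers count as event-free, they do not exclude Kaplan-Meier (which also yields a cumulative proportion), and an estimator for a secondary curve is often left to a statistical analysis plan, which is not at hand. The denominator is indeed open, and the reading restricted to people tested at that visit removes the bias for seroconversion if dropout is unrelated to infection. That part stands. It does not dispose of the point. The protocol states what each measure is, as a proportion of participants, beside an incidence measure that does use observation time. The readings shown give about 13%, 17% or 21% from the same data. Restricting to attenders also does not help seroreversion, where staggered entry alone lowers the figure to 16.5%.

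Two stronger readings are tempting and go too far. A reader might infer that all 37% who leave are counted as event-free. Those who were positive before leaving are counted correctly; only events after the last test are lost. A reader might also infer that seroconversion as quoted is understated by a fifth. That figure belongs to new events among baseline negatives. The quoted wording does not exclude baseline positives, and they dilute the relative error.

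It is also fair to say that no test, decision or primary objective rests on these curves. Spread is judged by prevalence at successive times and by person-days incidence.

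**Conclusion.** The point holds for the definitions as worded, with a size that depends on the reading.

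- **Seroconversion, literal reading over all participants.** New events among baseline negatives are understated by about 21-22%; the quoted measure by about 10-16% at 10% prevalence. Both assume a constant 1-5% risk per round, dropout unrelated to infection and ten visits. If only those tested at each visit are counted, there is no such bias under these assumptions.
- **Seroreversion.** This is the firmer half. Among ever-positives the proportion is 14.4% against a 36-week risk of 24.0% at the assumed rates, and it is too low even without dropout. No person-time measure is planned to back it up.

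The documents do not support a claim that the infection-spread results are distorted. The person-days incidence rate already accounts for dropout. This is a worthwhile correction to secondary descriptive measures, not a threat to the primary objective.

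**What to change.** In section 5.3.2, Cohort study:

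1. Define the at-risk sets: participants negative at the first test for seroconversion, and ever-positives, followed from their first positive test, for seroreversion.
2. Estimate both by Kaplan-Meier or an interval-censored equivalent, censoring each person at the last antibody test. Events are seen only between visits, and section 3.1 allows delayed tests, which favours the interval-censored form.
3. Show the number at risk at each visit.
4. If the proportion ever positive, baseline positives included, is still wanted, report it under its own name with its denominator stated.

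The cost is wording and a modest change of analysis. Test dates are already needed for person-days, so no new data are collected. Intervals at late visits become slightly wider. Censoring still assumes that dropout is unrelated to infection, and the text should say so.
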